## Protocol Amendment Summary of Changes Table

Document History		
Document	Version Date	Summary of Changes and Rationale
Amendment 2	23 Sep 2020	
Title page: Updates made to reflect addition of non-diabetic adults with obesity.
 
Rationale: This study population has been updated with Amendment 2.
 
Section 1.2, Schema: updated to indicate that participant-provided metformin is in participants with T2DM.
 
Rationale: Requirement for background metformin use is only applicable to T2DM participants.
 
Section 1.3, Schedule of Activities: footnote “b” added to table to indicate that regular fingersticks are not required in participants with obesity without T2DM but the glucometer and supplies should be dispensed as a backup in case they have signs or symptoms of hypoglycemia. Added mental health questionnaires (C-SSRS and PHQ-9) due to inclusion of participants with obesity.
 
Rationale: Safety monitoring approach has been updated due to addition of non-diabetic participants with obesity.
 
Section 2, Introduction: updated to indicate that clinical development in obesity is also planned.
 
Rationale: Update provides context for updated study population.
 
Section 2.1, Study Rationale: updated to reflect inclusion and rationale for participants with obesity and without T2DM, in addition to the addition of the higher target dose of 200 mg BID in 2 study arms.
 
Rationale: Updates provide rationale for updated study population and higher dose in 2 study arms.
 
Section 2.2.1, Nonclinical Safety: updated to include

	
exposure margins to the updated highest planned dose in this study of PF-06882961 200 mg BID.
 
Rationale: Updates align with higher dose in 2 study arms.
 
Section 2.2.2.2, Clinical Pharmacokinetics: updated to provide additional PK exposure information in participants without T2DM compared with participants with T2DM.
 
Rationale: Updates align with updated study population.
 
Section 3, Objectives and Endpoints: updated to reflect inclusion of participants with obesity and without T2DM.
 
Rationale: Updates align with updated study population.
 
Section 4.1, Overall Design and Figure 1: updated to reflect the following changes:
 

1. inclusion and rationale for participants with obesity and without T2DM;

2. Addition of Arm 5 (target dose of PF-06882961 200 mg BID) which will be administered to participants with T2DM and participants with obesity and without T2DM;

3. Increase in sample size for placebo arm and total study population.

 
Rationale: Updates provide rationale for updated study population and sample size, addition of 2 study arms and higher dose in 2 study arms.
 
Section 4.2, Scientific Rationale for Study Design and Section 4.3, Justification for Dose: updated to include rationale for inclusion of participants with obesity and without T2DM and rationale for addition of Arms 6 and 7 with target dose of PF-06882961 200 mg BID.
 
Rationale: Updates align with updated study population and higher dose in 2 study arms.
 
Section 5.1, Inclusion Criteria: updated to specify

--	--

	
inclusion criteria for all participants, criteria for participants with T2DM only and criteria for participants with obesity without T2DM. Also, minimum BMI for participants with T2DM has been increased to 27 kg/m^2 (with no upper limit for BMI), to provide a closer range to participants with obesity without T2DM.
 
Rationale: Updates align with updated study population.
 
Section 5.2.2. Exclusion Criteria All Participants: Added criteria numbers – 12. History of major depressive disorder or history of other severe psychiatric disorders (eg, schizophrenia or bipolar disorder) within the last 2 years; and criteria number 13. Any lifetime history of a suicide attempt. 17. A PHQ 9 score <math>\geq 15</math> obtained at V1, V2 or V3. 18.→ Response of “yes” to question 4 or 5, or on any behavioral question on the C-SSRS at V1, V2 or V3. These updates have been made based on the potential risk related to the product labeling for the injectable GLP-1R agonist liraglutide for obesity.
 
Rationale: Updates align with updated study population.
 
Section 5.3.1, Dietary Restrictions: updated to separate dietary guidelines for participants with and without T2DM.
 
Rationale: Updates align with updated study population.
 
Sections 6.1.1, Administration and 6.3.1 Allocation to Investigational Product: updated to indicate that with addition of Arm 6 and 7, Week 9 will also require 4 tablets BID to maintain the double blind across treatment arms. Table 2 was also updated to include titration scheme for Arm 6 and 7.
 
Rationale: Updates align with titration schemes required for the higher dose in the 2 additional study arms.
 
Section 6.6, Dose Modification: wording updated to

--	--

		
clarify that scheduled dose titration is used in active dosing regimens.
 
Rationale: Update clarifies that while doses are titrated over the study duration in the active arms, modification of the blinded dosing regimen is not permitted per protocol.
 
Section 8.2.4.1, Home Glucose Monitoring: updated to indicate that regular fingersticks are not required in participants with obesity without T2DM unless they have signs or symptoms of hypoglycemia.
 
Rationale: Updates align with updated study population.
 
Section 8.2.7, Mental Health Questionnaires and associated sub-sections have been added under Safety Assessments. Related sub-sections include: 8.2.7.1, Columbia Suicide Severity Rating Scale (C-SSRS), 8.2.7.1.1, Rater Qualifications, 8.2.7.2, Patient Health Questionnaire – 9 (PHQ-9) and 8.2.7.3, Referral to a Mental Health Professional.
 
Rationale: Updates to safety monitoring align with updated study population.
 
Section 9.1.1, Estimands, Section 9.3, Populations for Analysis and Section 9.4.1 Pharmacodynamic Analyses, updated wording.
 
Rationale: Updates clarify estimands and analyses pertaining to participants with T2DM and those pertaining to participants with obesity without T2DM.
 
Section 9.2, Sample Size Determination, increase in sample size for placebo arm and total study population.
 
Rationales: Updates reflect the changes in the study design.

Amendment 1	08 June 2020	Title page: EudraCT number in the original protocol was not correct and has been updated to Not Applicable, as this study will take place in the United States only.

	
Section 1.3. (Schedule of Activities), 8.7.2 (Banked biospecimens) and 8.8.2 (Biomarkers) change have been revised to incorporate Protocol Administrative Clarification Letter (dated 08 Oct 2019) to update the types of Biobank Samples collected.
 
Section 1.3, (Schedule of Activities) has been updated to add collection of banked biospecimens Prep B1.5 and B2.5 at the early termination visit.
 
Rationale: Collection of banked biospecimens at the early termination visit to allow for additional research in cases of early termination if applicable.
 
Section 2.2.1, Nonclinical Safety has been added to provide the most recent toxicology information. This section also includes the embryo-fetal toxicology data, which was previously in Section 4.2.
 
Rationale: Updates align with recently updated Investigator Brochure and all of the toxicology data are presented in the same section.
 
Sections 2.2.2 (Clinical Overview), 2.2.2.1 (Clinical Safety) and 2.2.2.2 (Clinical Pharmacokinetics) have been updated to reflect the completed C3421002 study.
 
Rationale: Updates align with the most recent clinical safety and pharmacokinetics information.
 
Section 4.2 and Appendix 8 (Prohibited Prior/Concomitant Medication) have been revised to list the exclusion of sulfasalazine, simplification regarding the use of potent CYP3A4 inhibitors and extension of timeframe prohibiting use of weight loss drugs.
 
Rationale: CCI [REDACTED] [REDACTED] Weight loss drug extension is to align with liraglutide restriction for glycemic control.
 
Section 4.3, Justification for Dose has been revised to reflect that study C3421002 has completed and data are no longer preliminary.
 
Rationale: C3421002 was completed after initial

--	--

	
protocol finalization.
 
Section 5.2, Exclusion Criteria, criterion #15 has been revised to lower the systolic and diastolic blood pressure eligibility criteria.
 
Rationale: The cut off for blood pressure has been lowered to a more conservative level to optimize blood pressure control prior to study entry.
 
Section 5.3.1, Dietary Restrictions has been revised to clarify that fasting is required prior to body weight (also a revision to Section 8.6.1 and Appendix 9) but is not required prior to post dose PK sample collection. Additionally, the requirement to withhold blood pressure and lipid modifying medications prior to site has been removed.
 
Rationale: Aligns with updates to Section 8.6.1 and Appendix 9, as body weight must be obtained under standardized conditions. Clarification that fasting is not required prior to post dose PK sample collection has been included given PF-06882961 is dosed with food. Blood pressure and lipid modifying medications may be taken prior to site visits to ensure blood pressure and lipid management is maintained in participants requiring these medications.
 
Section 6.4, Study Intervention Compliance has been updated to provide an example of how many doses may be missed for the placebo run-in duration, depending on differences in visit windows.
 
Rationale: Clarifies the compliance requirement for eligibility.
 
Section 6.5.4, Antihypertensive Medications has been revised to remove language regarding handling of participants who enter the study with a blood pressure of <math>\geq 160/100</math>.
 
Rationale: This language is no longer applicable given the revision to exclusion criterion #15.
 
Section 8.2.2.1, Blood Pressure and Pulse Rate has been revised to allow for manual assessment of BP and PR

--	--

		
only if an automated instrument is not available and also to clarify that the same arm for BP and PR should be used throughout the study, when possible.
 
Rationale: These revisions are made for clarification.
 
Section 8.3: (1) 8.3.1 Time Period and Frequency for Collection AE and SAE Information has been revised to remove the requirement for medical occurrences that begin before the start of study intervention but after obtaining informed consent to be recorded on the Medical History/Current Medical Conditions section of the CRF; (2) 8.3.1.2 Recording Nonserious AEs and SAEs on the CRF has been updated to reflect current sponsor language.
 
Rationale: This revision aligns with the requirement to collect and record all AEs and SAEs from the time informed consent is provided. It also aligns with current sponsor language regarding the recording of AEs and SAEs on the CRF.
 
Section 9.4.2.1, Electrocardiogram Analyses, has been revised to remove summarization of the number of participants with uncorrected QT values >500 msec.
 
Rationale: Safety analyses and summaries will be based on QTcF intervals, not QT intervals.
 
Section 9.4.3, Other Analyses has been revised to clarify that results from any future analyses from pharmacogenomic or biomarker data from banked biospecimens are not planned to be included in the CSR.
 
Rationale: These results are not routinely included in CSRs.
 
Protocol Appendix 4, Section 10.4.2, Female Participant Reproductive Inclusion Criteria the requirement of females to not donate eggs has been removed.
 
Rationale: This revision is made as PF-06882961 does not have risk of genotoxicity; as such the requirement of females to not donate eggs has been removed.

Original	27 September	N/A

PF-06882961

Protocol C3421008

Final Protocol Amendment 2, 23 September 2020

---

protocol	2019	
----------	------	--

This amendment incorporates all revisions to date, including Protocol Administrative Clarification letters (PACLS), and amendments made at the request of country health authorities and IRBs/ECs.

PFIZER CONFIDENTIAL

## 1. PROTOCOL SUMMARY

### 1.1. Synopsis

Not Applicable (N/A).

### 1.2. Schema

### 1.3. Schedule of Activities (SoA)

The SoA table provides an overview of the protocol visits and procedures. Refer to the **STUDY ASSESSMENTS AND PROCEDURES Section 8** of the protocol for detailed information on each procedure and assessment required for compliance with the protocol.

The investigator may schedule visits (unplanned visits) in addition to those listed in the SoA table, to conduct evaluations or assessments required to protect the well-being of the participant.

Protocol Phase (for abbreviations refer to Appendix 10 )	Screen	Run-in	Treatment Phase								Follow-Up		Early Term
Weeks Relative to Dosing on Day 1	-6 to -3	-2	0	2	4	6	8	10	12	13-14	16-17		ET
Days Relative to Dosing on Day 1	-42 to -15	-14±3	1	14±3	28±3	42±3	56±3	70±3	84±3	91-98	112-119 a		--
Visit	V1	V2	V3	V4	V5	V6	V7	V8	V9	V10	V11		ET
Informed consent & demography	x												
Review of eligibility criteria	x	x	x										
Open-ended inquiry for adverse events	x	→	→	→	→	→	→	→	→	→	x	x	
Medical history (update only at V2 and V3)	x	x	x										
Review prior or concomitant treatments	x	x	x	x	x	x	x	x	x	x	x	x	x
Review drug, alcohol/tobacco use	x	x	x	x	x	x	x	x	x	x	x	x	x
Review contraception use (females only)	x	x	x	x	x	x	x	x	x	x	x	x	x
Counseling on diet/exercise guidelines		x											
Dispense glucometer, supplies, diary, and provide training		x											
Review drug diary, glucometer & glucose log b			x	x	x	x	x	x	x	x	x		x
Glucose measurement (fasting, via glucometer, on site)		x	x	x	x	x	x	x	x	x	x		
Mental health questionnaires (C-SSRS, PHQ-9)	x	x	x	x	x	x	x	x	x	x	x		x
Physical examination (height at Screen only) c	x		x							x	x c		x
Body weight (in duplicate)	x	x	x	x	x	x	x	x	x	x	x		x
Supine vital signs assessment	x d	x	x d	x	x	x d	x	x	x	x d	x		x
Supine 12-lead ECG	x		x d	x	x	x d	x	x	x	x d	x		x
Registration in trial (via IRT)	x												
Randomization in trial (via IRT)			x										
Dispensation of IRT		x e	x f	x f	x f	x f	x f	x f	x f				
Witnessed dosing on site of IP (AM dose) – with food	x	x	x	x	x	x	x	x	x				
Compliance via pill count on site of returned IP		x	x	x	x	x	x	x	x				x
Blood Sampling for:													
-Fasting plasma glucose and HbA1c	x	x	x	x	x	x	x	x	x	x	x		x
-Hematology, chemistry (including eGFR)	x		x	x	x	x	x	x	x	x	x		x

PFIZER CONFIDENTIAL

Protocol Phase (for abbreviations refer to Appendix 10 )	Screen	Run-in	Treatment Phase								Follow-Up		Early Term
			0	2	4	6	8	10	12	13-14	16-17		
Weeks Relative to Dosing on Day 1	-6 to -3	-2	0										ET
Days Relative to Dosing on Day 1	-42 to -15	-14±3	1	14±3	28±3	42±3	56±3	70±3	84±3	91-98	112-119a		--
Visit	V1	V2	V3	V4	V5	V6	V7	V8	V9	V10	V11		ET
-FSH (females only), C-peptide	x												
-Pregnancy test (females only)	x	x	x	x	x	x	x	x	x	x	x		x
Lipids, TSH, free T4, calcitonin, amylase, lipase, TBA, PT/INR/aPTT	x		x		x		x		x	x	x		x
-PF-06882961 PK (pre-dose unless noted)			x g	x	x	x g	x	x	x g				x
-Banked biospecimen: Prep B1.5 & B2.5				x		x			x				x
-Banked biospecimen: Prep D1 (only Day 1) h			x										
Urine Sampling for:													
-Urine drug test	x												
Urinalysis (and microscopy, reflexive)	x		x			x			x	x	x		x
-On-site urine pregnancy test (females only) i	x	x	x	x	x	x	x	x	x	x	x		x

- a. May be a telephone contact, or a visit to the clinic if deemed necessary by the investigator.
- b. For participants with obesity only, the review of the glucometer and glucose log should be completed if participants have signs or symptoms of hypoglycemia. Otherwise, regular glucometer monitoring at home is not required.
- c. Full physical examination performed according to the [SoA](#). A limited physical examination is performed at the follow-up visit and may be performed at non-specified visits if there are findings during the previous exam or new/open AEs, if appropriate and at investigator discretion.
- d. Triplicate assessments (see [Section 8.2.2](#)) will be measured at screening, and pre- and post-dose times at Visit 3, Visit 6 and Visit 9, when both pre-dose and post-dose PK measurements are obtained.
- e. On V2 only, IP reflects single-blind placebo; it is dispensed via IRT.
- f. For V3 through V8, IP is dispensed via IRT and reflects double-blind randomized PF-06882961 or placebo.
- g. PK samples collected pre-dose and within the window approximately 2-6 hours post dose.
- h. If not collected on the designated collection day, collect at the next available time point when biospecimens are being collected in conjunction with a participant visit.
- i. For V3 through V9, the test result must be reviewed and deemed acceptable (ie, negative), to continue participation in the study.

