## **7. DISCONTINUATION OF STUDY INTERVENTION AND PARTICIPANT DISCONTINUATION/WITHDRAWAL**

### **7.1. Discontinuation of Study Intervention**

In rare instances, it may be necessary for a participant to permanently discontinue IP. If a safety or tolerability concern arises, in particular if not responsive to symptomatic management, dosing with double-blinded IP may be stopped in an individual participant at investigator discretion.

If IP is permanently discontinued, the participant remains in the study and continues to follow all protocol specified visits and procedures according to the [SoA](#).

The site should notify the Sponsor Medical Monitor or Sponsor Clinician if the below criteria for permanent discontinuation are met.

Note that discontinuation of IP does not represent withdrawal from the study.

See the [SoA](#) for data to be collected at the time of intervention discontinuation and follow-up and for any further evaluations that need to be completed.

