#### **7.1.1. Criteria for Discontinuation**

Discontinuation of IP must occur for a participant meeting any of the following conditions:

- Criteria for a potential Hy's law case are met (see [Appendix 6](#)).
- Intent to become pregnant or pregnancy confirmed by serum beta human chorionic gonadotropin ( $\beta$ -hCG) testing.
- Based on mental health assessment as outlined in [Section 8.2.7](#), should be discontinued from dosing at the discretion of the investigator.

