### **7.2. Participant Discontinuation/Withdrawal From the Study**

A participant may withdraw from the study at any time at his/her own request, or may be withdrawn at any time at the discretion of the investigator for safety, behavioral, compliance, or administrative reasons.

At the time of discontinuing from the study, if possible, an early termination visit should be conducted. See the [SoA](#) for assessments to be collected at the time of early termination and follow-up and for any further evaluations that need to be completed.

The early termination visit applies only to participants who are randomized and then are prematurely withdrawn from the study. Participants should be questioned regarding their reason for withdrawal. The participant will be permanently discontinued both from the study intervention and from the study at that time.

If a participant withdraws from the study, he/she may request destruction of any remaining samples, but data already generated from the samples will continue to be available, and may be used to protect the integrity of existing analyses. The investigator must document any such requests in the site study records.

If the participant withdraws from the study and also withdraws consent (see below) for disclosure of future information, no further evaluations should be performed and no additional data should be collected. The sponsor may retain and continue to use any data collected before such withdrawal of consent.

When a participant withdraws from the study because of an SAE, the SAE must be recorded on the CRF and reported on the Clinical Trial (CT) SAE Report.

Lack of completion of all or any of the withdrawal/early termination procedures will not be viewed as protocol deviations so long as the participant's safety was preserved.

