## **8. STUDY ASSESSMENTS AND PROCEDURES**

The investigator (or an appropriate delegate at the investigator site) must obtain a signed and dated ICD before performing any study-specific procedures.

Study procedures and their timing are summarized in the [SoA](#). Protocol waivers or exemptions are not allowed.

Immediate safety concerns should be discussed with the sponsor immediately upon occurrence or awareness to determine if the participant should continue or discontinue study intervention.

Adherence to the study design requirements, including those specified in the [SoA](#), is essential and required for study conduct.

All screening evaluations must be completed and reviewed to confirm that potential participants meet all eligibility criteria. The investigator will maintain a screening log to record details of all participants screened and to confirm eligibility or record reasons for screening failure, as applicable.

Every effort should be made to ensure that protocol-required tests and procedures are completed as described. However, it is anticipated that from time to time there may be circumstances outside the control of the investigator that may make it unfeasible to perform the test. In these cases, the investigator must take all steps necessary to ensure the safety and well-being of the participant. When a protocol-required test cannot be performed, the investigator will document the reason for the missed test and any corrective and preventive actions that he or she has taken to ensure that required processes are adhered to as soon as possible. The study team must be informed of these incidents in a timely manner.

For samples being collected and shipped, detailed collection, processing, storage, and shipment instructions and contact information will be provided to the investigator site prior to initiation of the study.

The total blood sampling volume for individual participants in this study is approximately 276 mL. The actual collection times of blood sampling may change. Additional blood samples may be taken for safety assessments at times specified by Pfizer, provided the total volume taken during the study does not exceed 550 mL during any period of 60 consecutive days.

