### **8.2.6. Pregnancy Testing**

Pregnancy tests will be both urine and serum tests, and must have a sensitivity of at least 25 mIU/mL. Serum pregnancy test will be required for eCRF collection. Urine pregnancy test will be used for site reference until serum pregnancy result becomes available.

Pregnancy tests will be performed in all females at the times listed in the [SoA](#). Following a negative pregnancy test result at screening, appropriate contraception must be commenced and a second negative pregnancy test result will be required at the baseline visit prior the participant's receiving the IP. Pregnancy tests will also be done whenever one menstrual cycle is missed during the active treatment period (or when potential pregnancy is otherwise suspected) and at the end of the study. Pregnancy tests may also be repeated if requested by institutional review boards (IRBs)/ethics committees (ECs) or if required by local regulations.

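### Schedule of Activities footnote i makes a negative urine pregnancy test at V4 to V9 a condition of staying in the study, whereas Sections 7.1.1 and 7.1 stop only the drug on confirmed pregnancy and keep the participant in follow-up

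*Protocol*

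**What the plan says.** Footnote i in Protocol 1.3 is attached to the row for the on-site urine test in females; the blood pregnancy test row does not carry it. It states: "For V3 through V9, the test result must be reviewed and deemed acceptable (ie, negative), to continue participation in the study".

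Section 7.1.1 lists the conditions under which IP must be discontinued. One is: "Intent to become pregnant or pregnancy confirmed by serum beta human chorionic gonadotropin" testing. That list concerns IP, not the study. Section 7.1 gives the consequence: "If IP is permanently discontinued, the participant remains in the study" and follows all scheduled visits and procedures. It adds: "Note that discontinuation of IP does not represent withdrawal from the study".

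Section 8.2.6 makes the serum test the result entered in the eCRF and says: "Urine pregnancy test will be used for site reference until serum pregnancy result becomes available".

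Section 7.2 governs leaving the study early. Of a participant withdrawn after randomization it says: "The participant will be permanently discontinued both from the study intervention and from the study at that time". Its routes out are the participant's own request or the investigator's discretion. Neither Section 7.2 nor Appendix 4 makes pregnancy a mandatory reason to leave.

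**The concern.** At V3 the footnote causes no difficulty. The test comes before randomization and first dose, and Section 8.2.6 also requires a negative test at that point.

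From V4 to V9 the participant has already been randomized and dosed. A site with a confirmed pregnancy then has two instructions. The footnote makes study participation conditional on a negative test. Sections 7.1.1 and 7.1 say to stop IP and keep her in the study. A site that follows the footnote ends her scheduled visits, including adverse-event inquiry and safety assessments, in a trial whose primary endpoint is the incidence and severity of treatment-emergent adverse events. She would also be counted as a study withdrawal rather than an IP discontinuation, and withdrawn participants are not replaced (Protocol 4.1).

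**Working it through.** The documents give no figure to reproduce, so the check is a comparison of texts followed by simple date arithmetic.

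**Comparison for a serum-confirmed pregnancy at V4 to V9**

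| Question | Footnote i | Sections 7.1.1 and 7.1 |
|---|---|---|
| Test named | On-site urine | Serum |
| What ends | Participation in the study | IP only |
| Later scheduled visits | None, if applied as written | All, through Visit 11 |

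The clear conflict is in the second and third rows.

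**Effect on the secondary estimands.** Protocol 9.1.1 and SAP 2.1.2 and 2.1.3 censor FPG, HbA1c and weight values after IP discontinuation and treat them as missing. IP stops under either text, so the data entering the mixed model are the same. No estimand result changes.

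**Effect on safety follow-up.** Inputs:
- Nominal visit days from the SoA: V4 = 14, V5 = 28, V6 = 42, V7 = 56, V8 = 70, V9 = 84. Visit 11 falls on Day 112 to 119 and may be a telephone contact.
- Minimum active collection of adverse events: 28 days after the last dose (Protocol 8.3.1).
- Treatment-emergent window: 365 days after the last dose (SAP 3.5.1), so events found in later follow-up count towards the primary endpoint.

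Formula: follow-up at risk = Visit 11 day − (stop day + 28), taking the visit day as the last dose.

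| IP stopped at | Stop day + 28 | Follow-up at risk (days) | Scheduled visits remaining, through V11 |
|---|---|---|---|
| V4 | 42 | 112 − 42 = 70 to 119 − 42 = 77 | 7 |
| V5 | 56 | 56 to 63 | 6 |
| V6 | 70 | 42 to 49 | 5 |
| V7 | 84 | 28 to 35 | 4 |
| V8 | 98 | 14 to 21 | 3 |
| V9 | 112 | 0 to 7 | 2 |

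Each day by which the last dose precedes the nominal visit day adds one day to the gap, and each day after it removes one. The figures apply per affected participant. The documents state neither the number of women nor the performance of the urine test, so no frequency can be derived.

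**The case against.** The best defence is that the footnote, read in context, is an interim gate. Section 1.3 describes the SoA as an overview and sends sites to Section 8 for detail. Section 8.2.6 then makes urine a reference only until serum is available, and the SoA schedules a blood pregnancy test at the same visits, so confirmation is already under way. The footnote does not mention withdrawal or early termination. Section 8 also says: "Immediate safety concerns should be discussed with the sponsor immediately upon occurrence or awareness". A sensible site would hold IP, wait for serum and call the sponsor.

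Most of this stands for the choice between urine and serum. A reader might infer that the footnote permanently removes a woman on a false-positive urine test. At V4 that would cost 12 − 2 = 10 of the 12 treatment weeks and 5 of the 6 post-baseline time points. The documents do not support presenting this as the planned outcome. It requires acting before the serum result that Section 8.2.6 tells the site to await. It remains a secondary risk, on a literal reading only.

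The defence does not settle what happens after serum confirms pregnancy. The footnote's condition concerns the study, Section 7.1 says the participant stays, and following the reference to Section 8.2.6 does not resolve this. Nor can the footnote simply be set aside: Section 8 says that "Adherence to the study design requirements, including those specified in the" SoA is mandatory. That does not rank the SoA above Section 7, but it leaves the site with two binding instructions.

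Other limits are fair. Section 8.2.6 itself orders no action on the serum result; only Section 7.1.1 does. Having an exit rule outside Section 7.2 is not in itself an error, since Section 8.2.7.3 contains one for recurrent suicidal ideation or behavior. Pregnancy outcome is followed under Appendix 4 either way, and a related serious event that the investigator learns of later must still be notified under Section 8.3.1.

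**Conclusion.** Wrong as written, minor. For a pregnancy confirmed at V4 to V9, footnote i conditions staying in the study on a test she has failed, while Sections 7.1.1 and 7.1 stop IP and retain her. I am confident of that conflict.

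Its size is at most the loss of scheduled safety follow-up after the guaranteed 28 days, from 70 to 77 days for a stop at V4 down to 0 to 7 days at V9, plus a changed disposition category. This assumes that the site applies the footnote as written, that the last dose is on the nominal visit day, that she would otherwise attend through Visit 11, and that withdrawal does not include withdrawal of consent for further contact. The number affected is likely to be very small and cannot be estimated from the documents.

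A reader might also infer that the efficacy-type results are at risk. In a confirmed pregnancy they are not, because censoring at IP discontinuation gives the same model input under either instruction.

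**What to change.** Replace footnote i with:

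> At V3, the result must be negative before randomization. At V4 through V9, the result must be reviewed and negative before further IP dosing; if positive, hold IP pending the serum result (Section 8.2.6) and contact the medical monitor about restarting IP if serum is negative. Pregnancy confirmed by serum leads to permanent IP discontinuation under Section 7.1.1, and the participant remains in the study under Section 7.1.

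Restarting should be a decision with the medical monitor, not an automatic return to the scheduled week's dose. In Table 2, Arms 2, 6 and 7 move from 20 to 40 mg BID between Weeks 2 and 3, so an automatic restart could place a woman on a higher step after missed days. Section 6.6 allows no dose adjustment to soften that.

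The cost is one footnote in the next amendment and a note to sites. No test or visit is added, and sample size, randomization and estimands are unchanged. The downside is a few missed doses during a hold, which Section 6.4 already requires to be recorded in the CRF as dosing deviations. The safeguard against dosing in pregnancy is kept.
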